4.5.2. Replacement of Subjects

If the planned number of subjects do not complete the study or complete certain procedures, additional subjects will be enrolled at the Sponsor's discretion to ensure that at least 16, 16, and 8 evaluable subjects complete Parts A, B, and D of the study, respectively.

4.5.3. Subjects Lost to Follow-up Prior to Last Scheduled Visit

A minimum of 3 documented attempts must be made to contact any subject lost to follow-up at any time point prior to the final scheduled study visit on Day 337 (± 3 days) in Part A, Day 365 (± 3 days) in Part B, or Day 341 (± 3 days) in Part D of the study. At least 1 of these documented attempts must include a written communication sent to the subject's last known address via courier or mail (with an acknowledgement of receipt request) asking that they return to the study center for their final safety evaluations.

4.5.4. Dose Group Stopping Criteria

IP administration will be halted for all subjects in a dose group, as well as any subjects in an ongoing higher dose group if any of the following stopping criteria are met:

- a. Two subjects in a dose group experience a significant febrile reaction (defined as \geq Grade 2 fever [>39.0 °C] associated with systemic symptomatology [eg, body aches, malaise, nausea]) within 24 hours following administration of IP.
- b. Two subjects in a dose group experience a suspected moderate to severe allergic/hypersensitivity reaction, including but not limited to anaphylaxis, generalized rash, edema or bronchospasm possibly related to drug treatment.

To determine whether this dose group stopping rule has been met, the relevant data will be reviewed by the PSRC. The treatment assignment of one or more subjects may be unblinded at the request of the PSRC, as described in Section 3.4.1.2. Following this review, the PSRC will decide if the dose group and other ongoing higher dose groups will:

- Resume unchanged or
- Resume with modifications to the protocol or
- Be terminated.

The Sponsor is responsible for notifying the relevant regulatory authorities and the Investigator is responsible for promptly notifying the relevant IRB of the decision.

4.5.5. Part D Stopping Criterion

IP administration will be halted for all subjects in Part D if the following stopping criterion is met:

- a. Three subjects experience Grade 1 fevers (38.0 to 39.0 °C) associated with systemic symptomatology (eg, body aches, malaise, nausea) onset within 24 hours following administration of IP on ≥ 3 separate occasions.

To determine whether this dose group stopping rule has been met, the relevant data will be reviewed by the PSRC. The treatment assignment of one or more subjects may be unblinded at the request of the PSRC, as described in Section 3.4.1.2. Following this review, the PSRC will decide if the dose group and other ongoing higher dose groups will:

- Resume unchanged or
- Resume with modifications to the protocol or
- Be terminated.

The Sponsor is responsible for notifying the relevant regulatory authorities and the Investigator is responsible for promptly notifying the relevant IRB of the decision.

4.5.6. Study Stopping Criteria

IP administration will be halted for all subjects if any of the following stopping criteria are met:

- a. A subject experiences a Grade 4, life-threatening treatment-emergent AE or death that is considered probably or definitely related to IP by the Investigator
- b. Two or more subjects in a dose group experience 1 or more moderate or severe pulmonary exacerbations during the 5-week treatment period in Part B or through Day 11 (1 week post-5th dose) in Part D
- c. Two or more subjects in a dose group experience an absolute decrease in predicted FEV1 of at least 25 % compared to the baseline value (defined as the average of the Day -1 and Day 1 pre-dose values) during the 5-week treatment period in Part B or through Day 11 (1 week post-5th dose) in Part D that cannot be explained, in the opinion of the Investigator, by the underlying disease of CF and that is confirmed on 2 separate occasions at least 3 days apart
- d. Two or more subjects in the study experience a suspected serious allergic/hypersensitivity reaction, including but not limited to anaphylaxis, generalized rash or bronchospasm likely to be related to drug treatment
- e. Two or more subjects in a dose group experience a deterioration in liver function, as detailed below:
 - i. Elevation of ALT or AST to >5 x ULN in a subject regardless of baseline value
 - ii. Elevation of ALT or AST to >3 x ULN in a subject with a normal baseline or elevation of >3 x ULN from the subject's actual baseline if not normal, with the

appearance of fatigue, nausea, vomiting, right upper quadrant pain or tenderness, fever, rash, and/or eosinophilia (>5%).

- iii. Elevation of ALT or AST to >3x ULN in a subject with a normal baseline or elevation of >3x ULN from the subject's actual baseline if not normal, and total bilirubin >2x ULN or INR >1.5.

To determine whether these stopping rules have been met, all available data relating to the safety of the IP will be reviewed by the PSRC. The treatment assignment of one or more subjects may be unblinded at the request of the PSRC, as described in Section 3.4.1.2. Following this review, the PSRC will decide if the study will:

- Resume unchanged or
- Resume with modifications to the protocol or
- Be terminated.

The Sponsor is responsible for notifying the relevant regulatory authorities and the Investigator is responsible for promptly notifying the relevant IRB of the decision.

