3.4.1.2. Other Oversight Roles

The PSRC will have responsibility for the overall safety of the subjects participating in the study as well as for making key decisions in the conduct of the study. These are summarized below. All decisions by the PSRC must be documented in writing.

The PSRC will be notified of 2 occurrences of significant febrile reactions in different participants (defined as \geq Grade 2 fever [$>39.0^{\circ}\text{C}$] associated with systemic symptomatology [eg, body aches, malaise, nausea]) within 24 hours following administration of IP. The PSRC will also be notified of all serious adverse events deemed possibly, probably, or definitely related to investigational product in real-time and will receive treatment-emergent SAE listings following each dose group and may choose to receive more frequent SAE listings at any time during the study.

If dose group stopping criteria described in Section 4.5.4 or Part D stopping criteria described in Section 4.5.5 are met during the study, the relevant data will be reviewed by the PSRC.

Following this review, the PSRC will decide whether the dose group and other ongoing higher dose groups will continue or be terminated.

If study stopping criteria are met during the study, all available data relating to the safety of the IP will be reviewed by the PSRC. Following this review, the PSRC will decide whether the study will continue or be terminated (Section 4.5.6).

If an adverse event of special interest (AESI), as described in Section 8.1.8, is reported during the study, the PSRC will be notified by the Sponsor in real-time.

To ensure subject safety, the PSRC may request unblinding the treatment assignment(s) for an individual subject or for an entire dose group.

For example, if IP administration is halted based on the stopping criteria of the study, the subsequent safety review may necessitate unblinding a subject's treatment assignment; or the safety data for an individual subject or the dose group may be unblinded before making the decision to dose escalate (eg, to determine if a treatment-emergent AE occurred in a placebo subject or not).

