8.1.2. Relationship Categorization

Relationship of an AE or SAE to IP is to be determined by the Investigator based on the following definitions:

Relationship to IP	Definition
Not Related	Unrelated to IP.
Possibly Related	A clinical event or laboratory abnormality with a reasonable time sequence to administration of IP, but which could also be explained by concurrent disease or other drugs or chemicals.
Probably Related	A clinical event or laboratory abnormality with a reasonable time sequence to administration of IP, unlikely to be attributable to concurrent disease or other drugs and chemicals and which follows a clinically reasonable response on de-challenge. The association of the clinical event or laboratory abnormality must also have some biological plausibility, at least on theoretical grounds.
Definitely Related	The event follows a reasonable temporal sequence from administration of the IP, follows a known or suspected response pattern to the IP, is confirmed by improvement upon stopping the IP (de-challenge), and reappears upon repeated exposure (re-challenge). Note that this is not to be construed as requiring re-exposure of the subject to IP; however, the determination of definitely related can only be used when recurrence of the event is observed.

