8.2.2. Reporting Procedures

All SAEs must be reported by the Investigator to Rho Product Safety, through the EDC system, within 24 hours of the first awareness of the event. The Medical Monitor will be notified of the SAE by Rho Product Safety. In the event of a fatal or life-threatening SAE, the Investigator must contact the Medical Monitor immediately by phone. The SAE must also be entered into the EDC system as soon as possible to notify Rho Product Safety.

Medical Monitor:

[REDACTED]

Responsible Physician:

[REDACTED]

Note: The 24-hour reporting requirement for SAEs does not apply to reports of abuse, misuse, overdose, or medication errors (Section 8.1.6) unless they result in an SAE.

If there are any questions regarding the reporting of SAEs, the Investigator should contact Rho Product Safety. For protocol- or safety-related issues, the Investigator should contact the Medical Monitor.

Rho Product Safety:

SAE Help Line: [contact] or [contact]

Safety E-mail: [contact]

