8.2.7. Fatal Outcome

Any SAE that results in the subject’s death (ie, the SAE was noted as the primary cause of death) must have fatal checked as an outcome with the date of death recorded as the resolution date. For all other events ongoing at the time of death that did not contribute to the subject’s death, the outcome should be considered not resolved, without a resolution date recorded.

For any SAE that results in the subject’s death or any ongoing events at the time of death, unless another IP action was previously taken (eg, drug interrupted, reduced, withdrawn), the action taken with the IP should be recorded as “dose not changed” or “not applicable” (if the subject never received IP). The IP action of withdrawn should not be selected solely as a result of the subject’s death.

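### Read literally, the causality definitions in Protocol 8.1.2 keep a first-episode death from triggering 4.5.6(a), the only automatic halt that one subject can set off

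*Protocol*

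**What the plan says.** Protocol 4.5.6 lists five criteria, (a) to (e), that halt dosing for all subjects. Criterion (a) is met when "A subject experiences a Grade 4, life-threatening treatment-emergent AE or death that is considered probably or definitely related to IP by the Investigator". SAP 2.7 repeats it and does not redefine relatedness.

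Protocol 8.1.2 tells the Investigator to rate causality from a table of four categories: not related, possibly, probably and definitely related.

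- *Possibly related* covers an event with reasonable timing "but which could also be explained by concurrent disease or other drugs or chemicals".
- *Probably related* covers an event with reasonable timing that is "unlikely to be attributable to concurrent disease or other drugs and chemicals and which follows a clinically reasonable response on de-challenge". It must also be biologically plausible.
- *Definitely related* asks for improvement on stopping and reappearance on re-exposure. A note says that re-exposure need not be attempted, but adds that "the determination of definitely related can only be used when recurrence of the event is observed".

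Neither 8.1.2 nor 4.5.6 adapts these definitions for fatal events or limits the de-challenge element to cases where it can be assessed.

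**The concern.** The trigger in 4.5.6(a) is the Investigator's rating, and the rating is fixed by definitions written for events a subject survives. A subject who dies in a first episode shows no response to stopping the drug and cannot have a recurrence. Taken as written, the definitions withhold both triggering ratings from the gravest event the criterion names, whatever the strength of the causal evidence.

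What is at stake is whether a halt follows from the rule or from someone's discretion. The question matters most in Part D, where Protocol 3.2.3 provides for daily dosing without staggered enrolment.

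**Working it through.** No sample size, power or error rate bears on this point; Protocol 9.6 says the sample size has no statistical basis. The check is a count of criteria followed by a comparison of definitions.

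**1. Subjects needed to trigger each halt**

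| Criterion | Minimum subjects |
|---|---|
| 4.5.4(a), significant febrile reaction | 2 |
| 4.5.4(b), moderate to severe hypersensitivity | 2 |
| 4.5.5(a), Grade 1 fevers in Part D | 3 |
| 4.5.6(a), Grade 4 event or death | 1 |
| 4.5.6(b), pulmonary exacerbations | 2 |
| 4.5.6(c), FEV1 decrease | 2 |
| 4.5.6(d), serious hypersensitivity | 2 |
| 4.5.6(e), liver function | 2 |

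Total: 2 + 1 + 5 = 8 criteria. Seven need two or three subjects and one, 4.5.6(a), needs one. The individual rules in 4.5.1 stop only the subject concerned.

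**2. The 8.1.2 definitions applied to an event that otherwise qualifies** (reasonable timing, plausibility, no likely alternative cause)

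| De-challenge response seen | Recurrence seen | Probably met | Definitely met | 4.5.6(a) met |
|---|---|---|---|---|
| No | No | No | No | No |
| No | Yes | No | No | No |
| Yes | No | Yes | No | Yes |
| Yes | Yes | Yes | Yes | Yes |

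On a literal reading, a first-episode death falls in the first row. A Grade 4 event that improves after dosing stops falls in the third row and triggers the rule normally. A death that follows an earlier episode which improved and then recurred could reach the fourth row. The gap is therefore confined to first-episode deaths.

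**3. Re-exposure.** Planned MRT5005 subjects number 4 × 3 = 12 in Part A, 4 × 3 = 12 in Part B and 6 in Part D, 30 in all. The 12 in Part A (12/30 = 40%) receive one dose, so recurrence on re-exposure is impossible for them whatever the event.

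**4. Comparison within the protocol.** The hypersensitivity criterion 4.5.4(b) accepts a possible relationship. The escalation rule in 3.4.2 uses the same probable-or-definite bar as 4.5.6(a), but expressly sends possibly related Grade 3 events to case-by-case PSRC review. Section 4.5.6 has no such wording for a death rated below *probably related*.

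The chance of a missed halt cannot be calculated. The documents give neither an event rate nor any indication of how often Investigators would set the de-challenge element aside. If they never did, 4.5.6(a) would not fire on a first-episode death; if they always did, it would.

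**The case against.** The strongest reply is by elimination. For a death with good timing and no likely alternative cause, *not related* is wrong, *possibly related* describes an event with another explanation, and *definitely related* is barred. *Probably related* is the best fit left, and it triggers the halt. The wording also helps: *probably related* asks for a response on de-challenge, which is looser than the improvement required for *definitely related*. I accept that many Investigators would rate this way. They would, however, be waiving an element that the text joins with *and*, and nothing in 8.1.2 permits that.

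The second reply is that other safeguards exist, and this also largely stands:

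- Under 4.5.6, "To determine whether these stopping rules have been met, all available data relating to the safety of the IP will be reviewed by the PSRC".
- Under 3.4.1.2, "The PSRC will also be notified of all serious adverse events deemed possibly, probably, or definitely related to investigational product in real-time", so a death rated only *possibly related* still reaches the committee.
- Under 8.2.2, "In the event of a fatal or life-threatening SAE, the Investigator must contact the Medical Monitor immediately by phone".
- The PSRC and Sponsor may end Part D (3.2.3), and the Sponsor may suspend the study at any time (10.1.5).
- An independent data monitoring committee has a member on the PSRC (9.5).
- SAP 2.6 says the PSRC charter details the stopping criteria. The charter is not among the documents and may already deal with fatal events.

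These make a missed halt unlikely. They are notices, reviews or discretionary powers, and none is itself an automatic halt.

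Two stronger readings are tempting and should be resisted. One is that Protocol 8.2.7 confirms the gap, because it says "The IP action of withdrawn should not be selected solely as a result of the" subject's death. That section tells sites how to complete the action-taken field for a fatal event; it does not govern causality, and it allows for an action taken before death. The other is that dosing in Part D would simply continue. If all 8 subjects started together and one MRT5005 subject died after dose 1, the remaining 7 would have 7 × 4 = 28 doses scheduled on Days 2 to 5, of which 5 × 4 = 20 would be MRT5005. That figure needs simultaneous starts, a rating that does not trigger the rule, and four days of inaction by everyone told of the death. With no overlap in dosing it is 0. The conclusion needs neither argument.

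**Conclusion.** The point holds as a drafting defect. Read literally, 8.1.2 denies a first-episode death both ratings that 4.5.6(a) accepts, and 4.5.6(a) is the one criterion of 8 that a single subject can trigger and the only one that names death. The defect is limited to the death limb. A reader might infer that the criterion is inoperative or that the trial has no means of stopping after a death; the documents support neither, because Grade 4 events that improve can still trigger it and the discretionary routes are real.

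The conclusion rests on taking the de-challenge element as a requirement, which its wording supports but practice may not follow, and on the PSRC charter not already covering the case. No event rate is assumed. No planned table is affected: the overall adverse event shells in the SAP show only related and not related. This is a cheap improvement.

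**What to change.** Add one sentence to Protocol 8.1.2, or a note to 4.5.6(a): for a fatal event the de-challenge and re-challenge elements do not apply, and a death with a reasonable time sequence, biological plausibility and no likely alternative cause is rated at least *probably related*. The wording of criterion (a) in the protocol and in SAP 2.7 can stay. Check the PSRC charter and align it if needed. The sponsor's clinicians and the PSRC should confirm the wording.

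Keep the sentence to fatal events. Extending it to non-fatal events after a single or last dose would alter the rating rule for all of Part A, and would move the threshold in 3.4.2, which counts Grade 3 events rated probably or definitely related.

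The cost is a minor amendment, with the Sponsor and IRB approval that 10.3.2 requires, and possibly an occasional extra temporary halt, which the PSRC can lift under 4.5.6. There are no added subjects, visits, procedures or analyses.
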